6.2.1 Health Action Process Approach Model Measure

This survey will examine psychological factors that may affect PA participation. The survey will be recorded either electronically or with pen and paper depending on the respondent's preference. Survey will take approximately 25 minutes to complete, and will assess constructs related to exercise such as perceived risks, self- efficacy, planning, and social support. The demographics questionnaire will also be administered with this measure.

6.2.2 Semi-Structured Interview:

A semi-structured interview will be conducted at the end of the intervention to understand what components were and were not effective. Data will not be recorded. This feedback will be used to improve future iterations of the intervention.

Tertiary Outcome Measure: Arterial stiffness

6.3.1 Pulse Wave Velocity

aPWV (m/s) is calculated by dividing the distance between measurement sites, by the pulse transit time. Distance between the carotid and femoral arteries will be measured using measuring tape along the surface of the body, held parallel to the testing table. The pulse transit is determined from the arterial blood pressure waves, which are collected at each arterial site. A pen-like device (model SPT-301; Millar Instruments Inc., Houston, TX) will be applied to the carotid and femoral arterial sites using a light pressure to obtain arterial pressure waves. Heart rate will be recorded using a single-lead (lead I) electrocardiogram (ECG) (model ML 123, ADInstruments Inc., Colorado Springs, CO).

Quaternary Outcome Measure: Cardiovascular and Fitness Parameters

6.4.1 Arterial structure: Wall thickness and lumen diameter

Carotid arterial images will be collected using B-mode ultrasound (INFO) for 10 cardiac cycles. Images will be analyzed using internal ultrasound software to determine lumen diameter and intima-media thickness.

6.4.2 Flow mediated dilation

A tight cuff will be placed on the upper 1/3 of the forearm and will be inflated to 200mmHg for 5min to occlude blood flow. The brachial artery diameter and blood velocity will be measured 1-minute prior to cuff inflation, 30 seconds before cuff deflation, and for the subsequent 3 minutes following cuff deflation.²⁴ The vasodilatory response will be assessed using wall-tracking software capable of continuously assessing vessel diameter and blood flow velocity.

6.4.3 Cardiac structure and function

Cardiac images will be collected non-invasively using Doppler ultrasound (Vivid q, GE Healthcare, Buckinghamshire, UK). Briefly, apical four and two-chamber views, and parasternal short and long-axis views will be collected and stored on the ultrasound for offline analysis. Indices of interest will include volumes (end systolic (ESV), end diastolic (EDV)), diameters (intraventricular septum systole (IVSs) and diastole (IVSd), left ventricular internal diameter systole (LVIDs)), systolic function (left ventricular posterior wall systole (LVIDd) and diastole (LVPWd), ejection fraction (EF), cardiac output (CO), fractional shortening, mitral regurgitation (dP/dT)) and diastolic function (E/A, E/e' ratio, IVRT, DT).

6.4.4 Aerobic Fitness Evaluation: Peak oxygen uptake test (VO2peak)

Participants will perform a graded arm ergometer test on an electronically braked arm ergometer (Angio Rehab arm ergometer, Lode, Groningen, the Netherlands), height adjusted so that the shoulder joint is aligned with the crank axis of the ergometer. Blood pressure (Dinamap Carescape V100; GE Healthcare, Buckinghamshire, UK) and respiratory measures (Quark CPET, Cosmed, Rome, Italy) will be collected two minutes prior to exercise. Heart rate will be recorded at one-second intervals via a chest strap heart rate monitor (Garmin, Schaffhausen, Switzerland). For participants with tetraplegia who have limited handgrip function, gloves (Active Hands, Solihull, Great Britain) will be used to secure hands to the ergometer handles. Participants will be instructed to maintain a cycling rate of 50 revolutions per minute (rpm) for the duration of the test. After an initial warm-up at 0W, power output will be increased each minute at a rate of 2-5 W/min for participants with tetraplegia, or 10 W/min for participants with paraplegia, until volitional exhaustion (i.e. dropping below 30 rpm). Ratings of perceived exertion (Borg 6-20 scale)²⁵ will be collected in the final 10-seconds of each stage. Oxygen consumption will be recorded on a breath-by-breath basis for the duration of the test and reported as rolling 30-second averages sampled at 5-second intervals as per consensus recommendations²⁶. This test is used to determine participants' peak oxygen uptake, ventilatory threshold and maximum heart rate.

6. ADVERSE EVENTS

Exercise will not be supervised by the interventionist, but physical activity recommendations will be made by a personal trainer. Participants will be advised that for up to 48 hours after exercise, the participant may experience delayed-onset muscle soreness as a result of performing strength training exercises. To minimize physical risks, the personal trainer will provide clear exercise instructions and training tips to ensure that proper technique and form are used. Participant feedback on the exercise perceived physical effort (mild, moderate or heavy) will be monitored weekly and the personal trainer will adapt the exercise plan as necessary to accommodate for this feedback.

A systematic review of adverse events reported in exercise interventions involving people with SCI was recently conducted. The limited adverse event data for upper-body training (aerobic or resistance) suggested that adverse events were rare, except for the occasional occurrence of musculoskeletal complaints.²⁷ Thus, it appears safe for adults with chronic SCI to exercise.

To minimize psychological and social risks in general, participants will be advised that their participation is completely voluntary, their data are completely anonymous, and that they may withdraw from the study at any time without penalty. In addition, to minimize mental strain, the research assistant will attempt to keep the physical activity coaching sessions to less than 15 minutes, allow participants to take breaks as needed and/or discontinue participation at any time during the session.

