Research Design: This study will employ a multi-centre, randomized, wait-list controlled trial. A total of 30 participants (15 experimental, 15 wait-list control) between 18-65 years of age who have chronic $SCI \ge 1$ year prior will be recruited. Physical activity measures will be taken using wrist-based accelerometers and the Physical Activity Recall Assessment for Persons with SCI. Psychosocial factors will be evaluated through questionnaires. The primary health outcome measure (aPWV), and secondary cardiovascular parameters will be assessed using a combination of echocardiography and ultrasound. Fitness will be determined using a peak oxygen consumption test on an armcycle ergometer. All measurement will be taken at baseline and after 9 weeks following intervention commencement. Physical activity will also be sampled mid-intervention at 4 and 7 weeks. For the wait-list control group, an additional measurement time point will be added after they have received the intervention upon completion of the control period. Training will involve weekly, 10-15 minute coaching sessions for 9 weeks. All pre- and post-assessments will take place at the Blusson Spinal Cord Centre at ICORD or the University of British Columbia Okanagan. Intervention content will be delivered over Skype or phone, and the wrist- worn accelerometers will be delivered and picked up from the participant's home during the intervention.

Statistical Analyses: Analyses will be conducted to determine the training (time), group (control vs experimental) and interaction (time x group) of all indices.

Table of Contents

SUN	/IMARY	. 2
Prea	amble	. 5
1.	BACKGROUND AND PROGRAM RATIONALE 1.1 Physical inactivity and spinal cord injury (SCI) 1.2 Physical inactivity and cardiovascular disease (CVD) in spinal cord injury (SCI) 1.3 The Health Action Process Approach and physical activity interventions in spinal cord injury.	5 5 5 d 6
2.	PURPOSE & HYPOTHESES	. 6
3.	RESEARCH DESIGN/ PROTOCOL	. 7
4.	RECRUITMENT	. 9
5.	OUTCOME MEASURES	10
Pi	rimary Outcome Measure: Physical activity 6.1.1: Physical Activity Recall Assessment for People with Spinal Cord Injury (PARA- SCI):	10 .10 .10
	6.1.2: 6-day Physical Activity Monitoring Period	10
	Measurement of energy expenditure during different sub-maximal wheeling speeds for calculation of moderate-vigorous physical activity during the 6-day physical activity	
	monitoring period	11

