Participants' motivation to exercise will first be determined according to stages of the HAPA model. Those who identify as pre-intenders (no intention to exercise) will receive intervention strategies that focus on changing motivation to be physically active. Those identified as intenders (willing to exercise but have not started) will focus on providing resources and behavioural strategies to commence physical activity. Lastly, those identified as actors (already exercising) will receive intervention strategies that help participants maintain or improve PA behaviour.

For those in the intender or actor stage, the intervention aims to promote the international SCI PA guidelines to promote fitness (at least 20 minutes of moderate vigorous aerobic activity twice/week and strength training twice/week). For those exceeding the fitness guidelines, the international SCI PA guidelines to promote health are promoted (at least 30 minutes of moderate to vigorous aerobic activity three times/week and strength training twice/week). However, these aims will be modified based on the individual's baseline PA. During the first visit, participants' baseline PA levels will be reviewed and an appropriate PA goal to achieve in the following month will be formed. In line with small changes PA goal setting, no pre-set goal grading strategies are established.²² In general, the goal of increasing daily PA by ten minutes on at least two days/week is provided as a guideline for grading the increase in goals. However, ultimately, the goal is the decision of the participant.

Following goal setting, barriers to participating in PA will be identified. The interventionist will select intervention strategies based on the identified barriers. A preformed chart of corresponding intervention strategies (e.g. use of behaviour change techniques, referral to facilities or peers, suggesting at-home exercises) was developed to aid this pairing process (Appendix A). These intervention strategies are accompanied by a comprehensive toolkit based from the HAPA model (Appendix B). In brief, the toolkit advises on three key strategies for promoting PA to people with SCI: i) education, ii) referral, iii) tailored PA prescription.

Remaining weekly coaching sessions will review participants' progress and barriers to discuss new goals and strategies as outlined above.

Control Participants:

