8. ADVERSE EVENTS

The study will be overseen and monitored by [name] (ICORD, Vancouver, BC Canada) and [name] [name] (UBC, Kelowna, BC Canada), who will visit their respective sites to examine trial procedures, ensure data quality, and monitor compliance with the study protocol.

Should an adverse event occur during exercise at the Vancouver or Kelowna site, subjects will be assisted by staff trained in emergency procedures. At the Vancouver site, defibrillators and resuscitation equipment will be in the training room at all times and if required physicians are within the building to provide emergency response. All exercise sessions in Vancouver are implemented on a hospital site where the VGH Emergency Department is nearby ([name]). At the Kelowna site, defibrillators and resuscitation equipment are located in the adjacent lab (ARTS 183), 911 will be dialed in case of on an emergency, and if needed will be transported to Kelowna General Hospital ([name]- 15-20 minutes via ambulance). There is also on-campus advanced life support team who have a fast (<5 minute) response time. Their [contact]) is located in the lab if needed. The researcher is certified in CPR C.

Autonomic Dysreflexia (AD)

AD is a common complication with SCI at or above the sixth thoracic level (T6) and is caused by loss of cardiovascular control. AD can be a life-threatening condition if not recognized and treated properly. Symptoms include: pronounced hypertension (rapid 20-40 mm Hg systolic rise); bradycardia or tachycardia; pounding headaches; anxiety; changes in vision; nasal congestion; sweating; goose bumps; and flushed skin. When reporting cases of AD, severity will be classified into mild, moderate and severe cases, based on observed symptoms. In the event that moderate to severe AD is suspected during testing sessions, the investigator will follow the steps outlined below:

- I. Have the participant sit upright or raise their head 90 degrees
- II. Take off or loosen any tight or restrictive clothing
- III. Monitor blood pressure every 2-3 minutes if hypertensive
- IV. Empty bladder and check for kinks and blockages if using an indwelling catheter

- V. Check skin for new wounds, pressure ulcers, burns, cuts, insect bites etc.
- VI. Check for any other negative stimulus below the lesion level

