- VII. If no stimulus is found and blood pressure does not change in 2 minutes, call for medical assistance and ambulance (Dial 88 for emergency response in Vancouver General Hospital, 911 in Kelowna).

Orthostatic Hypotension (OH)

OH is a common complication of SCI where the individual is unable to maintain homeostatic blood pressure during a change in body position. Symptoms include: lightheadedness and loss of consciousness. In the event OH is suspected during testing sessions, the investigator will follow the steps outlined below:

- i. Have the participant lie down in the supine position and monitor blood pressure every 2 minutes
- ii. If consciousness does not return within 5 minutes, call for medical assistance (Dial 88 for emergency response in Vancouver General Hospital, 911 in Kelowna)

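### No systematic collection of adverse events is described, either for the unsupervised exercise that the coaching promotes or for events at the sites

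*Combined protocol and SAP*

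**What the plan says.** **The exercise.** Section 6 (Adverse Events): "Exercise will not be supervised by the interventionist, but physical activity recommendations will be made by a personal trainer". The strategies listed in Section 3 include referral to facilities or peers and "suggesting at-home exercises". On how the coaching reaches participants, the Summary says "Intervention content will be delivered over Skype or phone"; Section 3 also allows face-to-face sessions.

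**The response to events.** The second Adverse Events section (numbered 8, placed before Section 7) says: "Should an adverse event occur during exercise at the Vancouver or Kelowna site, subjects will be assisted by staff trained in emergency procedures". Its steps for autonomic dysreflexia (AD) begin "In the event that moderate to severe AD is suspected during testing sessions", and those for orthostatic hypotension (OH) begin "In the event OH is suspected during testing sessions". The same section states that "All exercise sessions in Vancouver are implemented on a hospital site".

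**What reaches exercise away from the sites.** Section 6 provides a soreness warning, technique instructions and this: "Participant feedback on the exercise perceived physical effort (mild, moderate or heavy) will be monitored weekly", with the trainer adapting the plan in response. Section 3 has the weekly sessions review progress and barriers and has them audio-recorded.

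**Controls.** Section 3 gives them baseline and post-test assessment only during the control period. They then receive the same coaching, and the post-test measures are repeated.

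**The concern.** The intervention is encouragement to exercise more, so the exposure of interest for harm is about nine weeks of exercise that study staff do not watch. The protocol itself names the events to expect. Section 6 says the adverse-event data for upper-body training are limited and reports occasional musculoskeletal complaints. The second Adverse Events section calls AD common with injuries at or above T6 and potentially life-threatening, and calls OH a common complication.

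If nothing requires these events to be asked about and written down, the investigators learn of them only when a participant happens to mention one. Two things follow:

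- A low or zero count could not be told apart from a failure to ask.
- The coached arm has weekly opportunities to mention a problem and the control arm does not, so any by-arm difference would partly reflect contact frequency.

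Unlike a missing analysis detail, this cannot be repaired once the data are in.

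**Working it through.** The plan states no adverse-event rate or safety figure, so there is nothing to reproduce. The check is a comparison of the text, followed by a short illustration.

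**1. Each element against what it captures**

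| Element | Where | Reaches off-site exercise? | Asks about or logs events? |
|---|---|---|---|
| Emergency assistance | Second Adverse Events section | No: exercise at the two sites | Response only |
| AD steps | Same | No: testing sessions | Severity classes from observed symptoms; no form, period or recipient |
| OH steps | Same | No: testing sessions | Response only |
| Soreness warning, technique advice | Section 6 | Yes | No: prevention |
| Weekly perceived effort | Section 6 | Yes | Effort grade only, used to adapt the plan |
| Weekly coaching session | Section 3 | Yes | Progress and barriers; audio-recorded, no extraction of events described |
| Exit interview | 6.2.2 | Possibly | Its data are not recorded |

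The outcome list in Section 5 and the analyses in Section 8 (Data Analysis) contain no safety outcome. No section gives an adverse-event definition, a scheduled question, a form, a collection period or a reporting route. The gap therefore covers on-site events as well: the site text describes how to respond, not what to record.

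**2. Contact by arm in the first nine weeks.** Coached arm: 9 sessions (Section 7) plus baseline and post-test. Control arm: baseline and post-test only. The chance for an event to surface unprompted is unequal by design.

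**3. The exercise-location wording.** Read literally, the sentence placing all Vancouver exercise sessions on a hospital site conflicts with unsupervised and at-home exercise. It is consistent if it means only the treadmill wheeling and arm-ergometer tests.

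**4. Illustration: what a count of zero would mean.** With *n* exposed and every event captured, zero events gives a one-sided 95% upper limit of 1 − 0.05^(1/*n*):

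- *n* = 15 (experimental arm): 1 − 0.05^(1/15) = 0.181, or 18%.
- *n* = 30 (adding controls once coached): 1 − 0.05^(1/30) = 0.095, or 9.5%.

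If only a share *c* of affected participants is captured, the limit applies to the recorded risk, and the limit on the true risk is that value divided by *c*. For *n* = 30, assumed *c* = 0.5 gives 9.5%/0.5 = 19%, and assumed *c* = 0.25 gives 9.5%/0.25 = 38%. The plan gives no basis for any value of *c*.

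The chance of recording at least one affected participant among 30, at true risk *p*, is 1 − (1 − *pc*)^30, with *p* and *c* both assumed:

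| *p* | *c* = 1 | *c* = 0.5 | *c* = 0.25 |
|---|---|---|---|
| 5% | 0.785 | 0.532 | 0.314 |
| 10% | 0.958 | 0.785 | 0.532 |
| 20% | 0.999 | 0.958 | 0.785 |

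**The case against.** The strongest reply is that the plan does reach the unsupervised exercise. Section 6 deals with it directly, through instructions, a warning and weekly effort feedback that leads to changes in the plan. The weekly sessions review barriers, so a shoulder complaint that limits activity could well come up, and it would then be on a stored recording (Section 9). The text supplied is also incomplete: Appendices A and B, cited in Section 3, are not included, and consent pages, which might tell participants how to report problems, were removed. Finally, Section 6 describes events as rare apart from occasional musculoskeletal complaints, and none of the three hypotheses depends on safety data.

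Much of this stands. A reader might infer that the procedures cover on-site testing only, that perceived effort is the only weekly information, or that harms of the intervention would go unrecorded. The documents support none of these. The site text speaks of exercise as well as testing, the weekly sessions collect more than effort, and some harms could surface in them. Nor does the Vancouver sentence show that the planners assumed supervised training, since the sites do host exercise tests.

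What the reply does not supply is a step that makes asking and logging happen. An effort grade does not record an injury or an AD episode, and a recording from which no one is assigned to extract events is not a safety record.

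**Conclusion.** The concern holds in this form: the supplied text describes no systematic collection of adverse events, on-site or off-site, apart from severity classes for AD, and contact is unequal between arms. Spontaneous reports could therefore not be compared fairly, and a count of zero would say nothing about harm. The stronger conclusion, that harms would necessarily be missed, does not follow.

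The size cannot be estimated from the documents because they give no event rate. Even perfect capture with no events would exclude only risks above 18% (15 exposed) or 9.5% (30 exposed); with unknown capture neither limit can be claimed. The figure of 30 assumes that every control goes on to be coached and that nobody drops out. The finding also assumes that the absent appendices and consent pages contain no event-collection procedure. The planned efficacy analyses are unaffected. The change is worth making because it is cheap and the information cannot be recovered later.

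**What to change.** - **Ask.** Put one fixed event question, covering the types the protocol names (musculoskeletal complaints, AD, OH, other), at every existing weekly coaching contact, including the controls' later coaching period. At the week-9 post-test, ask both arms the same question about the preceding nine weeks.
- **Log.** Record date, severity and relation to exercise.
- **Report.** Give the week-9 counts by arm. Separately, give the weekly counts for all coached participants (up to 30).
- **Reconcile.** Bring the sentence on Vancouver exercise sessions into line with Sections 3 and 6, for example by stating whether it refers to testing sessions only.

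**Cost.** About 1–2 minutes per existing contact, one form page and one table. No visit is added, and the sample size and primary analysis do not change. One limitation remains: weekly asking may prime recall in the coached arm, so the week-9 comparison is still imperfect and should be described that way.

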8. ADVERSE EVENTS

The study will be overseen and monitored by [name] (ICORD, Vancouver, BC Canada) and [name] [name] (UBC, Kelowna, BC Canada), who will visit their respective sites to examine trial procedures, ensure data quality, and monitor compliance with the study protocol.

Should an adverse event occur during exercise at the Vancouver or Kelowna site, subjects will be assisted by staff trained in emergency procedures. At the Vancouver site, defibrillators and resuscitation equipment will be in the training room at all times and if required physicians are within the building to provide emergency response. All exercise sessions in Vancouver are implemented on a hospital site where the VGH Emergency Department is nearby ([name]). At the Kelowna site, defibrillators and resuscitation equipment are located in the adjacent lab (ARTS 183), 911 will be dialed in case of on an emergency, and if needed will be transported to Kelowna General Hospital ([name]- 15-20 minutes via ambulance). There is also on-campus advanced life support team who have a fast (<5 minute) response time. Their [contact]) is located in the lab if needed. The researcher is certified in CPR C.

Autonomic Dysreflexia (AD)

AD is a common complication with SCI at or above the sixth thoracic level (T6) and is caused by loss of cardiovascular control. AD can be a life-threatening condition if not recognized and treated properly. Symptoms include: pronounced hypertension (rapid 20-40 mm Hg systolic rise); bradycardia or tachycardia; pounding headaches; anxiety; changes in vision; nasal congestion; sweating; goose bumps; and flushed skin. When reporting cases of AD, severity will be classified into mild, moderate and severe cases, based on observed symptoms. In the event that moderate to severe AD is suspected during testing sessions, the investigator will follow the steps outlined below:

- I. Have the participant sit upright or raise their head 90 degrees
- II. Take off or loosen any tight or restrictive clothing
- III. Monitor blood pressure every 2-3 minutes if hypertensive
- IV. Empty bladder and check for kinks and blockages if using an indwelling catheter

- V. Check skin for new wounds, pressure ulcers, burns, cuts, insect bites etc.
- VI. Check for any other negative stimulus below the lesion level
- VII. If no stimulus is found and blood pressure does not change in 2 minutes, call for medical assistance and ambulance (Dial 88 for emergency response in Vancouver General Hospital, 911 in Kelowna).

Orthostatic Hypotension (OH)

OH is a common complication of SCI where the individual is unable to maintain homeostatic blood pressure during a change in body position. Symptoms include: lightheadedness and loss of consciousness. In the event OH is suspected during testing sessions, the investigator will follow the steps outlined below:

- i. Have the participant lie down in the supine position and monitor blood pressure every 2 minutes
- ii. If consciousness does not return within 5 minutes, call for medical assistance (Dial 88 for emergency response in Vancouver General Hospital, 911 in Kelowna)

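### The orthostatic hypotension steps tie the call for help to 5 minutes without return of consciousness, and nothing elsewhere requires a call at the moment consciousness is lost

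*Combined protocol and SAP*

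**What the plan says.** The protocol, section 8 (Adverse Events), under Orthostatic Hypotension (OH), describes a person with OH as "unable to maintain homeostatic blood pressure during a change in body position". It adds: "Symptoms include: lightheadedness and loss of consciousness". When OH is suspected in a testing session, the investigator is to follow two steps.

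- Step i: "Have the participant lie down in the supine position and monitor blood pressure every 2 minutes".
- Step ii: "If consciousness does not return within 5 minutes, call for medical assistance", by dialling 88 in Vancouver or 911 in Kelowna.

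The opening part of section 8 sets out general arrangements. For both sites: "Should an adverse event occur during exercise at the Vancouver or Kelowna site, subjects will be assisted by staff trained in emergency procedures". Vancouver has defibrillators and resuscitation equipment in the training room, and physicians in the building if needed. Kelowna has the same equipment in an adjacent lab, and "911 will be dialed in case of on an emergency". The Kelowna text also says: "There is also on-campus advanced life support team who have a fast (<5 minute) response time". The researcher holds CPR C certification.

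**The concern.** The protocol foresees that a participant may faint during testing, yet it attaches the call for help to the end of a wait and not to the faint. The steps begin on suspicion of OH, so a collapse from another cause that is first taken for OH would follow the same path. During the wait the only ordered activity is measuring blood pressure, and no reading leads to a call.

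The stake is participant safety in the small number of cases where consciousness does not come back quickly. Staff working from a numbered list can be expected to act on the number it gives. No endpoint, error rate, sample size or analysis is touched.

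**Working it through.** No statistical calculation applies, because the 5 minutes is a procedural threshold with no formula behind it. The check is to read the texts side by side and find which of them fixes the time of the call.

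1. **OH step i.** It orders lying flat and a reading every 2 minutes. On that schedule, readings fall at 2 and 4 minutes, both before the 5-minute point. Neither is linked to a call, and no breathing or pulse check is ordered.
2. **OH step ii.** The call is due when consciousness has not returned by 5 minutes. This is the only call trigger in the OH steps. The text does not say whether the clock starts at the faint or when the participant has been laid flat. If it is the latter, the unconscious time before the call would be somewhat more than 5 minutes.
3. **Trained-staff sentence.** It is worded for events during exercise. Section 3 places vascular and cardiac measures on Day 1 that are not exercise, and the protocol links OH to changes of position. A faint could therefore fall outside that sentence. Even where the sentence applies, it sets no time for a call.
4. **Kelowna 911 sentence.** It is not itself limited to exercise, and it supports an early call. It does not define an emergency or name unconsciousness.
5. **Vancouver physicians.** They are available if needed, with no stated trigger.
6. **Equipment, CPR certification and the on-campus team.** These are resources. None fixes when the call is made.

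Size of the delay, from the stated threshold:

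- Participant still unconscious at 5 minutes: call at 5 minutes under step ii, against 0 minutes if called at the faint. Difference: 5 − 0 = 5 minutes.
- Participant who wakes before 5 minutes: no call under step ii, one call if called at the faint. No time is gained.

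**The case against.** The strongest reply is that step ii sets a point by which a call must be made and does not forbid an earlier one. An unresponsive participant is an emergency on any ordinary reading, so the Kelowna 911 sentence and the Vancouver physicians already support calling at once, and a CPR-certified researcher would probably check breathing unprompted. That stands: a reader might infer that the protocol bars staff from calling before 5 minutes, and the documents do not support this. What remains is that an earlier call is permitted and not required, while the instruction written for this event names 5 minutes.

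Three other stronger readings are also unsupported.

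- **That 5 minutes is shown to be clinically wrong.** The documents contain no standard that it breaches. The autonomic dysreflexia steps call for help after 2 minutes of unchanged blood pressure, but that clock follows several earlier steps and concerns a condition the protocol describes as potentially life-threatening. The two thresholds are not parallel.
- **That the wait delays every responder in Kelowna.** Step ii names only 911 there. The on-campus team is a separate resource to which no wait is attached, so adding 5 minutes to its response time describes a scenario the protocol does not set. The figure "15-20 minutes via ambulance" leaves out ambulance arrival and time on scene, so total times to hospital cannot be derived.
- **That a number of harmed participants can be given.** The documents give no rate of fainting, and none for remaining unconscious at 5 minutes, which is the only group that would gain time.

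**Conclusion.** The point holds as a wording gap in a safety procedure. The OH steps contain one call trigger, set at 5 minutes without return of consciousness. They order no breathing or pulse check, and the general arrangements do not require a call when consciousness is lost. For a participant who stays unconscious, literal compliance can put the call 5 minutes later than necessary. For anyone who recovers sooner, no time is lost.

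This rests on two assumptions: that staff follow the numbered step as written, and that the clock starts at the faint. Whether the interval is too long is for the responsible clinician to decide. The equipment, physicians, on-campus team and CPR-certified researcher reduce the risk. I rate this a cheap improvement, with medium confidence.

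**What to change.** Replace OH step ii with:

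*ii. If the participant loses consciousness, keep them supine, check breathing and pulse, and call for medical assistance immediately (88 in Vancouver; 911 and the on-campus advanced life support team in Kelowna); continue blood pressure readings every 2 minutes until help arrives.*

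The responsible clinician should confirm the wording before it is used. Step i can stay as it is.

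The cost is one reworded step and a short staff briefing. The downside is an occasional unneeded call-out for a brief faint that resolves by itself. How often that would happen cannot be estimated from the documents. Data collection, sample size and analysis do not change.
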